6.5 Sponsor Responsibility for Reporting Adverse Events

All Adverse Events will be reported to regulatory authorities, IRB/IECs and investigators in accordance with all applicable global laws and regulations.

7. PHARMACEUTICAL INFORMATION

The investigator shall take responsibility for and shall take all steps to maintain appropriate records and ensure appropriate supply, storage, handling, distribution and usage of investigational product in accordance with the protocol and any applicable laws and regulations.

7.1 Product Descriptions

7.1.1 Description

7.1.1.1 Pembrolizumab Description

Pembrolizumab is a humanized anti-PD-1 mAb of the IgG4/kappa isotype with a stabilizing S228P sequence alteration in the fragment crystallizable (Fc) region. Pembrolizumab binds to human PD-1 and blocks the interaction between PD-1 and its ligands. The theoretical molecular weight of the polypeptide is 146,288 Da and its theoretical pI is 7.5. Additional information on pembrolizumab nomenclature is detailed in the following table:

Code Name	MK-3475 (Anti-PD-1)
Other Code Name	MK3, 02P106, ORG 307448-0, SCH 900475 (Anti-PD-1)
Chemical Name	Humanized X PD-1-mAb (H409A11) IgG4
CAS Number	1374853-91-4
CAS Name	Anti-(human protein PDCD1 (programmed cell death 1)) immunoglobulin G4 (human-Mus musculus monoclonal heavy chain) disulfide with human-Mus musculus monoclonal light chain, dimer
Trade Name	KEYTRUDA®

7.1.1.2 Trebananib Description

Trebananib is a novel Fc fusion protein directed against Ang1 and Ang2, expressed recombinantly in *Escherichia coli* (*E coli*). The molecule is a non-glycosylated homodimer engineered by fusing an immunoglobulin G1 (IgG1) Fc domain to 4 copies of an anti-Ang1 / anti-Ang2 peptide. Each monomeric unit contains 10 cysteine residues that are involved in 4 intrachain disulfide bonds and 2 interchain disulfide bonds. Trebananib contains 287 amino acids. The molecular weight is approximately 63.5 kDa.

7.1.2 Form

7.1.2.1 Pembrolizumab Form

Two drug product (DP) dosage forms are available for pembrolizumab: a white to off-white lyophilized powder, 50 mg/vial, and a liquid, 100 mg/vial, both in Type I glass vials intended for single use only. The drug products are manufactured using facilities and practices under Good Manufacturing Practice (GMP) requirements.

Pembrolizumab Powder for Solution for Infusion, 50 mg/vial is a lyophilized powder that is reconstituted with sterile water for injection prior to use. It is manufactured using either the fully formulated DS or the partially formulated DS. The fully formulated DS uses L-histidine as a buffering agent, polysorbate 80 as surfactant, and sucrose as stabilizer/tonicity modifier. Pembrolizumab DP using the partially formulated DS is formulated with L-histidine as a buffering agent, polysorbate 80 as a surfactant, and sucrose as a stabilizer/tonicity modifier, and may contain hydrochloric acid and/or sodium hydroxide for pH adjustment (if necessary).

Pembrolizumab Solution for Infusion 100 mg/vial is a liquid DP (manufactured using the fully formulated DS with L-histidine as a buffering agent, polysorbate 80 as a surfactant, and sucrose as a stabilizer/tonicity modifier).

Pembrolizumab will be provided by Merck as summarized in the following table:

Product Name & Potency	Dosage Form
Pembrolizumab 50 mg	Lyophilized Powder for Injection
Pembrolizumab 100 mg/ 4mL	Solution for Injection

7.1.2.2 Trebananib Form

Trebananib is provided as a sterile, preservative-free, lyophilized powder for reconstitution with sterile water for injection (sWFI) and dilution in normal saline (0.9% sodium chloride) for IV administration. Each sterile vial contains specified amount of deliverable drug product, that when reconstituted with a specified volume of sWFI contains an isotonic formulation of 30 mg/mL trebananib formulated with 10 mM histidine, 4% (weight/volume [w/v]) mannitol, 2% (w/v) sucrose, 10 mM arginine hydrochloride, and 0.01% (w/v) polysorbate 20 to a pH of 7.1. Each vial is for single use only. Lyophilized vials are manufactured in 4 presentations based on the deliverable drug product. The vial presentations, vial sizes, deliverable amount, and reconstitution volume are provided in the table below.

Vial Presentation	Vial size	Deliverable Amount	Reconstitution Volume (mL sWFI)
54 mg	5 cc	54 mg	2.0
150 mg	20 cc	150 mg	5.0
240 mg	20 cc	240 mg	8.0
600 mg	50 cc	600 mg	20.0

cc = cubic centimeters; mg = milligram; sWFI = sterile water for injection

7.1.3 Packaging and Labeling Information

Clinical supplies will be affixed with a clinical label in accordance with regulatory requirements.

7.1.4 Clinical Supplies Disclosure

This trial is open-label; therefore, the participant, the trial site personnel, the Sponsor and/or designee are not blinded to treatment. Drug identity (name, strength) is included in the label text; random code/disclosure envelopes or lists are not provided.

7.1.5 Storage, Handling, and Preparation Requirements

Clinical supplies must be stored in a secure, limited-access location under the storage conditions specified on the label. Receipt and dispensing of trial medication must be recorded by an authorized person at the trial site. Clinical supplies may not be used for any purpose other than

that stated in the protocol.

7.1.6 Administration

7.1.6.1 Pembrolizumab Administration

Pembrolizumab 200 mg will be administered as a 30 minute IV infusion every 3 weeks. Sites should make every effort to target infusion timing to be as close to 30 minutes as possible. However, given the variability of infusion pumps from site to site, a window of -5 minutes and +10 minutes is permitted (i.e., infusion time is 30 minutes: -5 min/+10 min).

7.1.6.2 Trebananib

Trebananib should be administered on Day 1, 8, and 15 of each 21-day cycle after all procedures/assessments have been completed. Trebananib may be administered up to 2 days before or after the scheduled Day of each cycle due to administrative reasons (± 2 days).

The first dose of trebananib will be administered by IV infusion over a 60-minute period. If the initial dose administration is well tolerated, future administrations may be given over approximately 30 minutes (treatment cycle intervals may be increased due to toxicity as described in section 5). Trebananib will be administered immediately after Pembrolizumab.

7.1.7 Ordering

Investigative sites will order and acquire Pembrolizumab directly from Merck. Pembrolizumab will be supplied from an investigational supply.

Investigative sites will order and acquire trebananib directly from Amgen, Inc. Trebananib will be supplied from an investigational supply.

7.1.8 Accountability

The investigator, or a responsible party designated by the investigator, is responsible for keeping accurate records of the clinical supplies received from Merck and Amgen, the amount dispensed to and returned by the participants and the amount remaining at the conclusion of the trial agent using the NCI Drug Accountability Record Form (DARF) or another comparable drug accountability form.

7.1.9 Destruction and Return

Upon completion or termination of the study, all unused and/or partially used investigational product will be destroyed at the site per institutional policy. It is the Investigator's responsibility to arrange for disposal of all empty containers, provided that procedures for proper disposal have been established according to applicable federal, state, local and institutional guidelines and procedures, and provided that appropriate records of disposal are kept.

8. ADMINISTRATIVE AND REGULATORY DETAILS

8.1 Confidentiality

8.1.1 Confidentiality of Data

The investigator affirms to the Sponsor that information furnished to the investigator by the Sponsor will be maintained in confidence, and such information will be divulged to the institutional review board, ethics review committee (IRB/ERC) or similar or expert committee; affiliated institution and employees, only under an appropriate understanding of confidentiality with such board or committee, affiliated institution and employees. Data generated by this trial will be considered confidential by the investigator, except to the extent that it is included in a publication as provided in the Publications section of this protocol.

8.1.2 Confidentiality of Participant Records

By signing this protocol, the investigator agrees that the Sponsor (or Sponsor representative), IRB/ERC, or regulatory authority representatives may consult and/or copy trial documents in order to verify worksheet/case report form data. By signing the consent form, the participant agrees to this process. If trial documents will be photocopied during the process of verifying worksheet/case report form information, the participant will be identified by unique code only; full names/initials will be masked prior to transmission to the Sponsor. By signing this protocol, the investigator agrees to treat all participant data used and disclosed in connection with this trial in accordance with all applicable privacy laws, rules and regulations.

8.1.3 Confidentiality of Investigator Information

Information with respect to the investigator, and all sub-investigators and trial site personnel, may be used and disclosed for trial management purposes, as part of a regulatory submissions, and as required by law. This information may include:

- name, address, telephone number and e-mail address;
- hospital or clinic address and telephone number;
- curriculum vitae or other summary of qualifications and credentials; and
- other professional documentation.

Consistent with the purposes described above, this information may be transmitted to the Sponsor, and subsidiaries, affiliates and agents of the Sponsor, in your country and other countries, including countries that do not have laws protecting such information. Additionally, the investigator's name and business contact information may be included when reporting certain serious adverse events to regulatory authorities or to other investigators. By signing this protocol, the investigator expressly consents to these uses and disclosures. In order to facilitate contact between investigators, the Sponsor may share an investigator's name and contact information with other participating investigators upon request.

8.1.4 Confidentiality of IRB/IEC Information

The Sponsor is required to record the name and address of each IRB/IEC member that reviews and approves this trial. The Sponsor is also required to document that each IRB/IEC meets regulatory and ICH GCP requirements by requesting and maintaining records of the names and qualifications of the IRB/IEC members and to make these records available for regulatory agency review upon request by those agencies.

8.2 Compliance

8.2.1 Compliance with Financial Disclosure Requirements

Regulations, Financial Disclosure by Clinical Investigators (21 CFR Part 54). It is the Sponsor's responsibility to determine, based on these regulations, whether a request for Financial Disclosure information is required. It is the investigator's/sub-investigator's responsibility to comply with any such request. The investigator/sub-investigator(s) agree, if requested by the Sponsor in accordance with 21 CFR Part 54, to provide his/her financial interests in and/or arrangements with the Sponsor to allow for the submission of complete and accurate certification and disclosure statements.

The investigator/sub-investigator(s) further agree to provide this information on a Certification/Disclosure Form, commonly known as a financial disclosure form, provided by the Sponsor or through a secure password-protected electronic portal provided by the Sponsor. The investigator/sub-investigator(s) also consent to the transmission of this information to the Sponsor in the United States for these purposes. This may involve the transmission of information to countries that do not have laws protecting personal data.

8.2.2 Compliance with Law, Audit, and Debarment

The investigator agrees to conduct the trial in an efficient and diligent manner and in conformance with this protocol; generally accepted standards of Good Clinical Practice (e.g., International Conference on Harmonization of Technical Requirements for Registration of Pharmaceuticals for Human Use Good Clinical Practice: Consolidated Guideline and other generally accepted standards of good clinical practice); and all applicable federal, state and local laws, rules and regulations relating to the conduct of the clinical trial. The investigator also agrees to allow monitoring, audits, IRB/ERC review and regulatory authority inspection of trial-related documents and procedures and provide for direct access to all trial-related source data and documents. The investigator agrees not to seek reimbursement from participants, their insurance providers or from government programs for procedures included as part of the trial reimbursed to the investigator by the Sponsor. The investigator shall prepare and maintain complete and accurate trial documentation in compliance with Good Clinical Practice standards and applicable federal, state and local laws, rules and regulations; and, for each participant participating in the trial, provide all data, and, upon completion or termination of the clinical trial, submit any other reports to the Sponsor as required by this protocol or as otherwise required pursuant to any agreement with the Sponsor.

Trial documentation will be promptly and fully disclosed to the Sponsor by the investigator upon request and also shall be made available at the trial site upon request for inspection, copying, review and audit at reasonable times by representatives of the Sponsor or any regulatory authorities. The investigator agrees to promptly take any reasonable steps that are requested by the Sponsor as a result of an audit to cure deficiencies in the trial documentation and worksheets/case report forms. The investigator must maintain copies of all documentation and records relating to the conduct of the trial in compliance with all applicable legal and regulatory requirements. This documentation includes, but is not limited to, the protocol, worksheets/case report forms, advertising for participant participation, adverse event reports, participant source data, correspondence with regulatory authorities and IRBs/ERCs, consent forms, investigator's curricula vitae, monitor visit logs, laboratory reference ranges, laboratory certification or quality control procedures and laboratory director curriculum vitae. By signing this protocol, the investigator agrees that documentation shall be retained until at least 2 years after the last approval of a marketing application in an ICH region or until there are no pending or contemplated marketing applications in an ICH region or until at least 2 years have elapsed since the formal discontinuation of clinical development of the investigational product. Because the clinical development and marketing application process is variable, it is anticipated that the retention period can be up to 15 years or longer after protocol database lock. The Sponsor will determine the minimum retention period and notify the investigator when documents may be destroyed. The Sponsor will determine the minimum retention period and upon request, will provide guidance to the investigator when documents no longer need to be retained. The sponsor also recognizes that documents may need to be retained for a longer period if required by local regulatory requirements. All trial documents shall be made available if required by relevant regulatory authorities. The investigator must consult with and obtain written approval by the Sponsor prior to destroying trial and/or participant files. ICH Good Clinical Practice guidelines recommend that the investigator inform the participant's primary physician about the participant's participation in the trial if the participant has a primary physician and if the participant agrees to the primary physician being informed. The investigator will promptly inform the Sponsor of any regulatory authority inspection conducted for this trial. Persons debarred from conducting or working on clinical trials by any court or regulatory authority will not be allowed to conduct or work on this Sponsor's trials. The investigator will immediately disclose in writing to the Sponsor if any person who is involved in conducting the trial is debarred or if any proceeding for debarment is pending or, to the best of the investigator's knowledge, threatened. In the event the Sponsor prematurely terminates a particular trial site, the Sponsor will promptly notify that trial site's IRB/IEC.

8.2.3 Compliance with Trial Registration and Results Posting Requirements

Under the terms of the Food and Drug Administration Modernization Act (FDAMA) and the Food and Drug Administration Amendments Act (FDAAA), the Sponsor of the trial is solely responsible for determining whether the trial and its results are participant to the requirements for submission to the Clinical Trials Data Bank, <http://www.clinicaltrials.gov>. Information posted will allow participants to identify potentially appropriate trials for their disease conditions and pursue participation by calling a central contact number for further information on appropriate trial locations and trial site contact information.

8.3 Quality Management System

By signing this protocol, the Sponsor agrees to be responsible for implementing and maintaining a quality management system with written development procedures and functional area standard operating procedures (SOPs) to ensure that trials are conducted and data are generated, documented, and reported in compliance with the protocol, accepted standards of Good Clinical Practice, and all applicable federal, state, and local laws, rules and regulations relating to the conduct of the clinical trial.

8.4 Data Management

The investigator or qualified designee is responsible for recording and verifying the accuracy of participant data. By signing this protocol, the investigator acknowledges that his/her electronic signature is the legally binding equivalent of a written signature. By entering his/her electronic signature, the investigator confirms that all recorded data have been verified as accurate. Detailed information regarding Data Management procedures for this protocol will be provided separately.

9. STUDY CALENDAR

Baseline evaluations are to be conducted within 28 days prior to start of registration except where noted otherwise. In the event that the participant's condition is deteriorating, laboratory evaluations should be repeated within 48 hours prior to initiation of the next cycle of therapy.

Assessments must be performed prior to administration of any study agent. Study assessments and agents should be administered within ± 2 days of the protocol-specified date, unless otherwise noted.

Screening and Induction							
Trial Period:	Induction						
Treatment Cycle/Title:	Screening Visit	Cycle 1 ^J			Cycles 2, 3, and 4 ^J		
Scheduling Window (Days):	-28 to -1	1 \pm 2	8 \pm 2	15 \pm 2	1 \pm 2	8 \pm 2	15 \pm 2
Informed Consent	x						
Inclusion/Exclusion Criteria	x						
Demographics and Medical History	x						
Prior and Concomitant Medication Review	x	x	x	x	x	x	x
Pembrolizumab Administration		x			x		
Trebananib Administration (induction phase only for 12 weeks) ^I		x	x	x	x	x	x

A Phase Ib Study to test the safety and potential synergy of pembrolizumab (anti-PD-1) and AMG386 (angiopoietin-2 (Ang-2) in patients with advanced solid tumors

Version 5.0– August 12, 2021

Review Adverse Events		x	x	x	x	x	x
Physical Examination	x	x	x	x	x	x	x
Vital Signs and Weight	x	x	x	x	x	x	x
ECOG Performance Status	x	x	x	x	x	x	x
Single EKG	x						
HIV, Hepatitis C Antibody, Hepatitis B Surface Antigen	x						
Pregnancy Test – Serum β -HCG ^A	x	x	x	x	x	x	x
PT/INR and aPTT	x	x	x	x	x	x	x
CBC with Differential	x	x	x	x	x	x	x
Comprehensive Serum Chemistry Panel, lipase and amylase	x	x	x	x	x	x	x
Tumor markers: CEA and CA125 ^H		x			x		
Urinalysis ^B	x	x			x		
T3, FT4 and TSH	x	x	x	x	x	x	x
Chest, Abdomen and Pelvic CT scan ^C	X ^E						x
Brain MRI ^D	X ^E						x
Archival or Newly Obtained Tissue Collection ^F	x						X
Correlative Studies Blood Collection ^G		x	x	x			

Post-Induction

Trial Period:	Post Induction
Treatment Cycle/Title:	Cycles 5 and beyond for up to 2 years total
Scheduling Window (Days):	Day 1 (\pm 2)
Prior and Concomitant Medication Review	x
Pembrolizumab Administration	x
Review Adverse Events	x
Physical Examination	x
Vital Signs and Weight	x

ECOG Performance Status	x
Pregnancy Test – Urine ^A	x
PT/INR and aPTT	x
CBC with Differential	x
Comprehensive Serum Chemistry Panel, lipase and amylase	x
Tumor markers: CEA, CA125H	x
Urinalysis ^B	x
T3, FT4 and TSH	x
Chest, Abdomen and Pelvic CT scan ^C	x
Brain MRI ^D	x
Correlative Studies Blood Collection ^G	x

Post Treatment

	Post-Treatment			
Treatment Cycle/Title:	End of Treatment Visit	Safety Follow-up	Follow Up Visits	Survival Follow-Up
Scheduling Window (Days):	At time of Discontinuation	30 days post discontinuation (± 3)	Every 12 weeks post discontinuation (± 7) for at least a year	Every 12 weeks (± 7)
Prior and Concomitant Medication Review	x	x		
Post-study anticancer therapy status			x	X
Survival Status				x
Review Adverse Events	x	x	x	
Physical Examination	x	x	x	
Vital Signs and Weight	x	x	x	
ECOG Performance Status	x	x	x	
CBC with Differential	x	x		

Comprehensive Serum Chemistry Panel, lipase and amylase	x	x		
Urinalysis ^B		x		
T3, FT4 and TSH		x		
Chest, Abdomen and Pelvic CT scan ^C	x		x	
Brain MRI ^D	x		x	
Archival or Newly Obtained Tissue Collection ^G	x			
Correlative Studies Blood Collection ^G	x			

^A For women of child-bearing potential, a negative serum β -HCG pregnancy test must be performed during screening. A urine pregnancy test should be performed within 24 hours of starting treatment. A urine pregnancy test may be performed at all other timepoints. If a urine pregnancy test result is positive, a serum pregnancy test must be completed and resulted as negative for a participant to receive treatment.

^B Proteinuria will be monitored by urine protein: creatinine ratio at least every six weeks. If appropriate, 24-hour urine collection for protein may be obtained.

^C CT scan of the chest, abdomen, and pelvis will be performed every 12 weeks (\pm 7 days)

^D Brain MRI to be performed only on melanoma and RCC patients. Brain MRI should be performed during screening. Repeat brain MRI should be performed if there are any neurological symptoms or findings. Brain MRI with and without contrast is preferred. If a patient is not able to obtain an MRI, CT imaging with contrast is acceptable. If a patient is not able to receive IV contrast, CT head without contrast is acceptable.

^E Imaging for baseline tumor assessment is to be performed within 28 days prior to the start of study registration.

^F Biopsy of site(s) of pre-existing disease will be performed up to 6 weeks (42 days) prior to initiation of treatment on Day 1. On-treatment biopsies should be performed approximately midway through the Induction period, approximately 6 weeks from the start of study treatment (sometime between Cycle 2 Day 8 – Cycle 3 Day 1). If for any reason removal of tissue requires a greater procedure, the biopsy must be done >28 days from the last planned dose trebananib

^G Serial blood/serum samples to be collected prior to the administration of pembrolizumab at the following time points: Cycle 1 Days 1, 8, and 15; Prior to Day 1 of every odd cycle (Cycle 3, Cycle 5, Cycle 7, etc.); End of treatment visit.

^H Tumor markers: CEA to be done on participants with colorectal cancer on day 1 of every cycle. CA125 to be done on participants with ovarian cancer on day 1 of every cycle.

^I If trebananib is discontinued due to an AE, participants may omit any Day 8 and Day 15 visits/assessments going forward.

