5.14 Long-Term Follow-Up and Study Completion

Patients will be followed every 12 weeks after discontinuing study treatment.

Patients removed from study for unacceptable adverse event(s) will be followed until progression.

All patients will be followed for at least a year from the time of initiation of treatment or until death, whichever occurs first.

After documented disease progression each participant will be followed by telephone or medical record review for overall survival until death, withdrawal of consent, or the end of the study as detailed below.

Participants will be removed from study when any of the following criteria apply:

- Lost to follow-up
- Withdrawal of consent
- Death

The reason for taking a participant off study, and the date the participant was removed, must be documented in the case report form (CRF).

A ODQ Off Study Form will be filled out when a participant comes off study. This form can be found on the ODQ website or obtained from the ODQ registration staff.

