10.5.2 Follow-Up Visits

Participants who discontinue trial treatment for a reason other than disease progression will move into the Follow-Up Phase and should be assessed every 12 weeks (84 ± 7 days) by radiologic imaging to monitor disease status for at least 1 year. Every effort should be made to collect information regarding disease status until the start of new anti-neoplastic therapy, disease progression, death, end of the study or if the participant begins retreatment with pembrolizumab as detailed in Section 10.5.4. Information regarding post-study anti-neoplastic treatment will be collected if new treatment is initiated.

Participants who are eligible to receive retreatment with pembrolizumab according to the criteria in Section 11.3.4 will move from the follow-up phase to the Second Course Phase when they experience disease progression. Details are provided in Section 9 – Trial Flow Chart for Retreatment.

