11. MEASUREMENT OF EFFECT

11.1 Antitumor Effect – Solid Tumors

Although the clinical benefit of these drugs has not yet been established, the intent of offering this treatment is to provide a possible therapeutic benefit, and thus the patient will be carefully monitored for tumor response and symptom relief in addition to safety and tolerability. Patients with measurable disease will be assessed by standard criteria. For the purposes of this study, patients should be re-evaluated every 12 weeks (\pm 7 days). In addition to a baseline scan, confirmatory scans will also be obtained 4-6 weeks following initial documentation of an objective response.

Response and progression will be evaluated in this study using the new international criteria proposed by the Response Evaluation Criteria in Solid Tumors (RECIST) guideline (version 1.1)

[*Eur J Ca* 45:228-247, 2009]. Changes in the largest diameter (unidimensional measurement) of the tumor lesions and the shortest diameter in the case of malignant lymph nodes are used in the RECIST criteria.

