14.6 Efficacy Analysis

Secondary endpoints will be used to gain preliminary estimates of efficacy. The analyses of secondary endpoints will be based on patients enrolled in the expansion cohorts and will be summarized within disease type. ORR will be estimated for each disease cohort and will be summarized with 90% confidence intervals estimated using exact binomial methods. For samples of size 12, the confidence intervals will be no wider than 0.5. Time-to-event endpoints (i.e., PFS, OS, TTP) will be summarized using the product-limit method of Kaplan-Meier; confidence intervals will be based on log(-log(survival)) methodology. Six-month PFS, 12-month OS, and median TTP will be presented, by disease, with 90% confidence intervals. With few patients in each disease, statistical testing will be of low power. Therefore, the analyses within disease will be primarily descriptive and will not rely on p-values.

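### Follow-up CT scans are timed from the stop date, so some progression before 6 months in patients who stop without progression is dated after 6 months; the effect on 6-month PFS is small

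*Combined protocol and SAP*

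**What the plan says.** **Interval.** Section 11.1 sets the general rule: "For the purposes of this study, patients should be re-evaluated every 12 weeks", with a 7-day margin. Footnote C to the CT row of the section 9 calendar repeats the interval: "CT scan of the chest, abdomen, and pelvis will be performed every 12 weeks". On treatment this gives scans at weeks 12, 24 and 36.

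**After stopping.** The Post Treatment table marks CT in two columns. One is the End of Treatment visit, timed "At time of Discontinuation". The other is Follow Up Visits, timed "Every 12 weeks post discontinuation" for at least a year. Section 5.14 has the same anchor: "Patients will be followed every 12 weeks after discontinuing study treatment". Section 10.5.2 says "Participants who discontinue trial treatment for a reason other than disease progression will move into the Follow-Up Phase" and requires imaging every 84 ± 7 days, without naming the date from which to count. Under section 10.3.1.2, a patient who starts another anti-cancer therapy moves to survival follow-up.

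**Endpoints.** Section 14.5 measures PFS from the start of treatment to objective progression or death. Section 14.6 says: "Six-month PFS, 12-month OS, and median TTP will be presented, by disease, with 90% confidence intervals". Section 14.2 defines colorectal disease control as complete or partial response, or stable disease lasting at least 6 months, and rejects a 15% rate at 9 or more of 40. Section 11.1.5 runs stable disease from the start of treatment to progression. The best-response window in section 14.5, written for the objective response rate, closes at progression or when therapy ends.

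**The concern.** Scan dates determine when progression is recorded. If the scan clock restarts on stopping, two patients with the same tumour course can fall on opposite sides of 6 months because one stopped for a reason other than progression. For example, take progression at week 22. A patient still on treatment is scanned at week 24 and counts as an event before 6 months. A patient who stopped at week 20, progression-free at the End of Treatment CT, is next scanned at week 32 and counts as progression-free at 6 months.

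Six-month PFS is a stated secondary endpoint, reported by disease in small cohorts. Duration of stable disease also enters the colorectal disease control rate, which is judged by a count, so one reclassified patient can matter near the cut-off.

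**Working it through.** **Inputs.** From the documents: scans every 12 weeks; a CT at the stop date; follow-up visits with CT every 12 weeks from the stop date; disease control rule of at least 9 of 40, 15% against 30%, one-sided alpha 0.1, stated power 85%. Assumed: 6 months = 182.625 / 7 = 26.1 weeks; exponential time to progression; the stop rates below.

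**1. The plan's own figure.** With the null variance, the critical count is 40 × 0.15 + 1.2816 × √(40 × 0.15 × 0.85) = 8.89, so reject at 9. Power is Φ[(0.15 − 1.2816 × √(0.15 × 0.85/40)) / √(0.30 × 0.70/40)] = 85.8%, which agrees with the stated 85%. By exact binomial calculation, the rule has power 88.9% and type I error 0.135.

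**2. Scan dates by stop week, reading the calendar literally.**

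| Stop (week) | Last scan by 26.1 weeks | Next scan | Progression moved past 6 months |
|---|---|---|---|
| 1–2 | 25–26 | 37–38 | none; slightly more is caught |
| 4 | 16 | 28 | weeks 16–24 |
| 8 | 20 | 32 | weeks 20–24 |
| 12 | 24 | 36 | none |
| 13–14 | 25–26 | 37–38 | none; slightly more is caught |
| 15 | 15 | 27 | weeks 15–24 |
| 18 | 18 | 30 | weeks 18–24 |
| 22 | 22 | 34 | weeks 22–24 |

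The shift occurs when stop week + 12 exceeds 26.1, that is, for stops after about week 14.1 and before week 24. It also occurs for stops at about weeks 2.1 to 12. Those patients must in addition be progression-free at an intervening scan, so the chance for each such patient is lower.

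**3. Effect within the affected group.** Take patients progression-free at a stop uniform over weeks 12 to 24, with λ = ln 2 / median.
- On the grid, the share with progression dated by 6 months is 1 − (1 − e^(−12λ)) / (12λ).
- With the clock restarted, only stops up to week 14.1 have a scan in time. The share is (26.09 − 24)/12 × (1 − e^(−12λ)).

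| Assumed median (weeks) | On the grid | Clock restarted | Difference (points) |
|---|---|---|---|
| 8 | 37.8% | 11.3% | 26.5 |
| 13 | 26.1% | 8.2% | 17.9 |
| 20 | 18.2% | 5.9% | 12.3 |

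**4. Effect on the whole cohort.** A simulation assigned 5%, 10% or 20% of patients a stop without progression, uniform over weeks 0–24 or 14.1–24. Median time to progression was 10, 17 or 26 weeks. All patients stayed in imaging and none died. Both schedules included the End of Treatment CT. The rise in observed 6-month PFS ran from 0.29 points (5%, weeks 0–24, median 26) to 1.72 points (20%, weeks 14.1–24, median 17).

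A check by formula for 20%, weeks 14.1–24, median 10 (λ = 0.0693):
- The mean of e^(−λs) over weeks 14.1 to 24 is (0.3763 − 0.1895)/(0.0693 × 9.9) = 0.272.
- The rise is 0.20 × (0.272 − 0.1895) = 0.0165, against 0.0168 simulated.

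**5. Disease control, only if such cases count as control.** The exact probability of 9 or more of 40 is 0.135 at 15%. It is 0.157 at 15.5%, 0.180 at 16% and 0.230 at 17%.

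**The case against.** **The anchor is arguably open.** Footnote C and sections 10.5.2, 11.1 and 11.1.6 give an interval and no start date. Section 5.12 keeps patients who stop early in study visits and procedures. A site could stay on the original grid. This stands in part: the text does not forbid the grid, but the only anchor it states after discontinuation is the stop date.

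**Stronger readings do not hold.** A reader might infer that every patient who stops loses the week-24 scan, or that the error always favours the treatment. The table in the working shows otherwise: a stop at week 12 keeps week 24, and stops at weeks 1–2 or 13–14 replace it with a scan at weeks 25–26. The End of Treatment CT also catches progression up to the stop.

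**Few patients may be affected.** Section 5.12 continues tumour assessments through dosing interruptions, so only discontinuation counts. Trebananib is planned to end at week 12. Patients who start new therapy leave imaging follow-up. The simulation ignores both that exit and deaths. These points stand, and they are why the conditional figures of 12 to 27 points must not be read as effects on the cohort.

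**Inflated colorectal disease control is not established.** If the window in section 14.5 governs, a patient who stops at week 20 may earn no 6-month credit at all. Section 14.8 equates 6 months of treatment with 24 weeks. On that reading, a patient on treatment with progression first seen at week 24 already has 24 weeks of stable disease, and the contrast disappears or turns on the 7-day margin.

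**Low stakes.** The primary objective is safety, and section 14.6 calls the within-disease analyses mainly descriptive. This limits the importance of the point but is no reason to leave the anchor as it is.

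**Conclusion.** The point holds for 6-month PFS. Following the calendar as written leaves no scheduled scan between the End of Treatment CT and 6 months for patients who stop without progression at about weeks 14 to 24 and stay in imaging follow-up. There is a smaller effect for stops at about weeks 2 to 12. The bias is mostly favourable and, across a cohort, small: about 0.3 to 1.7 percentage points. That range rests on exponential progression, assumed stop rates of 5% to 20%, complete imaging, no deaths and 6 months taken as 26.1 weeks.

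For colorectal disease control the effect is conditional. It needs stable disease to run to progression as in section 11.1.5, and 6 months to mean about 26 weeks. The documents settle neither, so they do not support a claim that the rate is inflated. This is a cheap improvement to the schedule, not a threat to the trial's main conclusions.

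**What to change.** - In the section 9 calendar (Follow Up Visits) and sections 5.14 and 10.5.2, state that imaging after discontinuation without progression stays on the original grid: every 12 weeks (± 7 days) from Cycle 1 Day 1, until progression or new anti-cancer therapy.
- Let a grid scan within 4 weeks before or after the End of Treatment visit serve as the End of Treatment scan.
- In sections 14.2 and 14.5, give 6 months in days and say which window governs disease control: to progression, or to the end of therapy.

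**Cost.** A few lines of text. Some scans will no longer coincide with the follow-up clinic visit. The allowance must run in both directions. Without it, a week-20 stop has scans at weeks 20, 24, 36, 48, 60 and 72 (six in the year after stopping), against 20, 32, 44, 56 and 68 (five) now. With it, the week-24 scan replaces the one at week 20 and the count returns to five.
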